10.7.4. Patient Discontinuation from the Study

Patient discontinuation prior to the patient's completion of the study is expected to be uncommon, occurring only if the patient explicitly withdraws consent. At the time of discontinuing from the study, the Medical Monitor should be contacted, and, if possible, an early discontinuation visit should be conducted, per the Study Schedule. The patient will be

permanently discontinued both from the IMP and from the study at that time. During the study closeout period, survival (vital) status will be collected within legal and ethical boundaries for all patients randomized who withdrew their participation from the study.

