7.2. Key Study Dates

7.2.1. Definition and Imputation of Key Event Dates

Date of End of Study (EOS): the study completion/early termination date recorded on the “Study Completion/Early Termination” CRF. Note that the patient may have a 30-day post EOS follow-up visit after this.

Date of Study Completion (DSC): For patients who did not complete the study, it is the later of a) the date of EOS and b) the date of the 30-day post EOS follow-up visit. For patients who completed the study, it is the latest date of a) the date of EOS, b) the date of the 30-day post EOS follow-up visit, or c) the date of death. This date is used to calculate the duration of study (follow-up) for each patient and all clinical events that happen during this period are adjudicated.

Date of First Dose of IMP (DFDOSE): for each patient, the DFDOSE is the date/time of administration recorded on the “On-Site Study Medication/ Compliance” CRF at Visit T1. If that field is missing, it is set to be next first date of administration at Visit T3.

Date of Last Dose of IMP (DLDOSE): the date of last dose is recorded on the End of Treatment CRF. In cases of missing either completely or partially, it is imputed as the earliest date of a) the last day of the month (if the month and year are present), or the last day of the year (if only the year is present); b) the Date of EOS; and c) the date of the last IMP dispense plus the number of tablets taken.

Date of Last Visit (DLVISIT): the last date recorded on either the *Visit Date* or the *Telephone Contact* CRFs. For patients who did not complete the study, this must be on or prior to the DSC.

Date of Last Known Alive (DALIVE): for patients whose vital status at the end of study is either alive or unknown, this is the last day when the patient is known to be alive. It is the latest “last known alive date” recorded on the *Survival Status* CRF. If this date is partially or completely missing, it is set to the later of last known alive date with imputation and DSC.

Date of Last Assessment for Non-Fatal Clinical Endpoints (DLASMT): Potential clinical endpoints are assessed every three months either in clinic or by telephone through the Post-EOS Phone visit. For patients who died during the study within 90 days of last visit, the DLASMT is set to the date of death. Otherwise, the DLASMT is set to be DLVISIT. Note that this definition also applies to new-onset diabetes mellitus (NODM) as an efficacy endpoint.

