Date of Last Survival Follow-Up (DLSFU): For patients who completed the study, or withdrew consent, or discontinued study and were identified as dead only through survival search (death is not adjudicated), it is the DSC. For all other patients it is the Date of Last Known Alive. This is the last date for survival status follow-up.

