7.2.5. Time to Event and Date of Censoring

For time-to-event analysis of clinical endpoint events (including new-onset type 2 diabetes), the start date is the date of randomization when the FAS is used, based on the ITT principle. When the PPS is used, the start date is set to be the date of first dose. For composite endpoints, the event date is the date of the first component event.

Patients who did not have any event in question will be considered as censored for the analysis. The date of censoring is determined as the following:

- Fatal events (CV death, fatal MI, fatal stroke, all-cause mortality): censored at Date of Last Survival Follow-Up.
- Non-fatal events and composite endpoints that include both fatal and non-fatal events: censored at the Date of Last Assessment.

Please see Section 18.3 for special censoring rule as applicable to patients from Ukraine as a result of the ongoing conflict.

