8.5. Missing Data Handling

For the primary analysis of the primary and key secondary endpoints, there is no imputation. All clinical endpoints, including the types and dates of events, are adjudicated by the Clinical Event Committee (CEC) with no missing types or dates. Time-to-event analyses are carried out based on the censoring rules outlined in Section 7.2.5.

For other analyses involving missing data, specific analysis methods or imputation rules are specified in the relevant sections as needed. If not specified, general rules specified in this section apply.

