15.1. Adjudicated Clinical Endpoints

Clinical events including death (CV or non-CV), nonfatal MI, nonfatal stroke, coronary revascularization, and hospitalization for unstable angina that occurred during the study are reviewed and adjudicated by the CEC in a blinded fashion as described in the Charter.

Positively adjudicated clinical events that occurred after randomization will be summarized by adjudicated event types and subtypes, and by treatment groups for the FAS. They are included in the analyses for the derivation of study endpoints (Sections 3.1, 3.2.1 and 3.2.2).

When a patient had multiple events of the same type (e.g., two coronary revascularizations) on the same day, only one event is counted in descriptive and recurrent event analyses.

All adjudicated deaths and non-fatal clinical events will be presented in listings with information from the adjudication forms.

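### For the mortality endpoints, a discontinued patient's censoring date depends on whether the closeout search finds the patient alive or dead, so the search can add survivor time but never a death

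*SAP*

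**What the plan says.** SAP 7.2.5 gives the rule for the mortality endpoints: "Fatal events (CV death, fatal MI, fatal stroke, all-cause mortality): censored at Date of Last Survival Follow-Up". SAP 7.2.1 defines that date. It is the date of study completion (DSC) for completers, for patients who withdrew consent, and for patients who "discontinued study and were identified as dead only through survival search (death is not adjudicated), it is the DSC". The next sentence covers everyone else: "For all other patients it is the Date of Last Known Alive". The Date of Last Known Alive is itself defined only "for patients whose vital status at the end of study is either alive or unknown". If it is partly or wholly missing, "it is set to the later of last known alive date with imputation and DSC".

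Three other provisions decide how this works:

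- For a non-completer, DSC is the later of the end-of-study date and the 30-day follow-up visit. The date of death can extend DSC only for completers (SAP 7.2.1).
- SAP 8.5 says that clinical endpoints "are adjudicated by the Clinical Event Committee (CEC) with no missing types or dates". SAP 15.1 builds the endpoints from "Positively adjudicated clinical events that occurred after randomization". A death that was not adjudicated is therefore not an event.
- SAP 4.3 has vital status collected at closeout, within legal and ethical limits, for every patient who did not complete the study.

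**The concern.** Take two patients who are formally discontinued on the same day without withdrawing consent and are both traced at closeout. The one found alive stays in the risk set, event-free, up to the last-known-alive date. The one found dead is cut back to DSC with no event. The censoring date therefore depends on the outcome being analysed, and in this group the hazard after DSC is zero by construction.

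CV death and all-cause mortality are steps 6 and 7 of the testing hierarchy (SAP 8.3), confirmatory only if every earlier step succeeds. Fatal MI and fatal stroke lie outside it. Three things could go wrong:

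- Absolute mortality is understated whenever some survivors are traced.
- If discontinuation without withdrawal differs by arm, the hazard ratio moves in favour of the arm with more of it.
- A mortality difference that arises after patients leave would not show in the hazard ratio.

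**Working it through.** **Who is affected.** The following fall outside the problem:

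- consent withdrawers, who go to DSC dead or alive (SAP 7.2.1);
- deaths within 30 days of discontinuation, which go to adjudication (Protocol 13.2.6);
- patients who died without having been discontinued, who count as completers, so that DSC includes the death date (SAP 7.1, 7.2.1);
- MACE-4, MACE-3, MI, coronary revascularization and stroke, which are censored at the last assessment date (SAP 7.2.5).

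What remains is formal discontinuation without consent withdrawal, followed by a death more than 30 days later that only the search finds.

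**Inputs from the documents.** 14,000 patients randomized 1:1, 33 months' enrolment and mean follow-up of 42 months (SAP 8.1), taken as uniform over 42 ± 16.5 = 25.5 to 58.5 months; two-sided alpha 0.05 (SAP 8.3). The plan states no mortality figure, so there is none to reproduce.

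**Assumptions not in the documents.** Mortality μ = 2%/yr, the same before and after leaving; leaving without withdrawal at λ = 0.1 to 2%/yr; exponential times; complete tracing unless stated; untraced patients end at DSC. The planned 1%/yr loss to follow-up is not a rate for this group.

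**Formulas.** For potential follow-up T and leaving at time u, let a = min(u + 30 days, T) and L = T − a. Per patient:

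- deaths lost = ∫ λ·exp(−(μ+λ)u)·exp(−μ(a−u))·[1 − exp(−μL)] du
- survivor time kept = ∫ λ·exp(−(μ+λ)u)·exp(−μ(a−u))·exp(−μL)·L du

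Both are averaged over T and multiplied by 7,000 per arm.

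**Balanced arms** (both arms together; 945 deaths if nobody leaves):

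| Leaving, %/yr | Deaths not counted | Death-free survivor PY kept | Rate per 100 PY (true 2.000) |
|---|---|---|---|
| 0.1 | 2 | 80 | 1.997 |
| 0.25 | 4 | 199 | 1.992 |
| 0.5 | 8 | 397 | 1.983 |
| 1 | 16 | 788 | 1.967 |
| 2 | 32 | 1,557 | 1.934 |

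The 1%/yr row in full: counted deaths 945 − 16 = 929; person-years to DSC 929/0.02 = 46,450; SAP rate 929/(46,450 + 788) = 1.967 per 100. With half of survivors traced it is 1.983; with none traced, 2.000. The null hazard ratio stays at 1.000 and type I error at 5.0%.

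**Unequal leaving, no true effect, 2 vs 1%/yr.** Halving the table rows gives the per-arm figures:

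- higher-leaving arm: (945 − 32)/2 = 456.5 deaths, 456.5/0.02 = 22,825 PY plus 778.5 survivor PY, rate 1.934;
- other arm: (945 − 16)/2 = 464.5 deaths, 23,225 PY plus 394 survivor PY, rate 1.967.

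The ratio is 0.983. With SE = √(1/456.5 + 1/464.5) = 0.066, the shift is 0.25 SE, so rejection is Φ(−1.96 + 0.25) + Φ(−1.96 − 0.25), about 5.7%.

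| Leaving, %/yr | Null HR | Type I error |
|---|---|---|
| 0.1 vs 0.2 | 0.998 | 5.01% |
| 0.25 vs 0.5 | 0.996 | 5.05% |
| 1 vs 1.25 | 0.996 | 5.05% |
| 1 vs 1.5 | 0.992 | 5.2% |
| 1 vs 2 | 0.983 | 5.7% |
| 1 vs 2, half of survivors traced | 0.992 | 5.2% |

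At 1% or 3%/yr mortality, 1 vs 2% leaving gives 0.983 (5.4%) and 0.984 (6.0%). For CV death at an assumed 60% of deaths it gives 0.983 (about 5.4%). Censoring every discontinued patient at DSC gives 1.000 and 5.0% in all these cases.

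**Simulation check** (8,000 trials of 14,000 patients per scenario, log-rank test, Monte Carlo SE 0.24 points): at 1 vs 2%/yr, rejection was 5.4% under the SAP rule and 5.0% under the DSC rule, with a paired HR ratio of 0.983. The shift in the hazard ratio is clear; the type I excess is close to simulation error.

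**Different mortality after leaving.** With 4 vs 2%/yr after leaving and 1%/yr leaving in both arms, the HR is 1.017 if found deaths count, 1.001 under the SAP rule and 1.000 under the DSC rule.

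**The case against.** The strongest counter-argument is that almost nobody is in the group. Protocol 10.7.4 says that leaving the study is "expected to be uncommon, occurring only if the patient explicitly withdraws consent", and withdrawers are treated alike dead or alive. At 0.1%/yr, which fits that expectation, 2 of 945 deaths are affected and a twofold imbalance gives an HR of 0.998, about 1/40 of a standard error. Terminations may also cluster near closeout, leaving little later time; if half are dated there, 1 vs 2%/yr leaving gives 0.992 and 5.2%. Nothing in the documents suggests unequal leaving in a double-blind trial. Deaths found by the search would still appear in the survival-status summary (SAP 9). SAP 18.3 and 18.4 are not in the supplied text and may hold relevant sensitivity analyses. Finally, cutting everyone at DSC discards lawful follow-up and does not reveal a mortality difference after leaving.

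The points on size stand: the effect may be very small, and the rates are assumptions. They do not rescue the rule. SAP 7.2.1 lists discontinuation separately from consent withdrawal, so it provides for the case. Lack of adjudication may justify leaving a death out, but it does not justify keeping the matching survivors' time. In the supplied text no other analysis covers this: the multiple-imputation and tipping-point analyses are for MACE-4 only (SAP 15.2.4, Appendix 6), and the per-protocol analysis uses the same methodology (SAP 15.4.1). The limit of the DSC rule is real, which is why the fix adds a sensitivity analysis.

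**Conclusion.** The concern holds. For CV death, fatal MI, fatal stroke and all-cause mortality, the SAP makes censoring of discontinued, non-withdrawing patients depend on the outcome. It should be fixed before unblinding, although it does not threaten the primary endpoint.

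Under the assumptions above, the mortality rate is understated by about 0.2% (relative) at 0.1%/yr leaving, 1.7% at 1%/yr and 3.3% at 2%/yr. With balanced leaving, the hazard ratio and type I error are essentially unchanged. With 2 vs 1%/yr leaving, the null hazard ratio moves to about 0.98, and at 2%/yr mortality the type I excess is under one percentage point. The reading of the text is firm. The size rests on mortality, leaving and tracing rates that neither document gives, and a relevant analysis in SAP 18.4 cannot be ruled out.

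**What to change.** Before unblinding, amend SAP 7.2.1 so that, for all four fatal endpoints, every discontinued patient is censored at DSC whether the search finds the patient alive, dead or not at all. Consent withdrawers stay at DSC as now. No new data are needed, since the SAP already derives DSC and falls back on it when the last-known-alive date is missing.

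Add one all-cause mortality sensitivity analysis that counts deaths found by the search at the date of death, where a date exists and may lawfully be used, and censors traced survivors at the last-known-alive date. Protocol 6.3 supports it: follow-up runs to study termination unless consent is withdrawn. Report tracing completeness by arm beside it, because this version errs the other way if deaths are traced more fully than survivors (1 vs 2%/yr leaving, all deaths but half of survivors traced: null HR 1.008).

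The cost is one sentence and one table. The primary mortality analysis gives up about 790 patient-years at 1%/yr leaving, none of which can hold a countable death. At a true HR of 0.85 both rules have 861 deaths and 66.2% power; at 2%/yr leaving, power is 65.5 vs 65.4%. The sensitivity analysis needs death dates, and the supplied text does not show whether they are collected.

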7.2.2. Reference Start Date and Study Day

Day 1 (Reference Start Date) is defined as the Date of First Dose of IMP, or the date of randomization for patients who did not receive any dose of IMP.

Study Day will be calculated from the reference start date (Day 1) as follows:

- If the date of the event is on or after the reference date, then: Study Day = (date of event – reference start date) + 1.
- If the date of the event is prior to the reference date, then: Study Day = (date of event – reference start date).

The Study Day will be used to show start/stop day of assessments and events (including AEs, prior and concomitant medications).

7.2.3. Baseline

For safety parameters, unless otherwise specified, baseline is defined as the last non-missing measurement taken on or prior to Day 1 (including unscheduled assessments).

Baseline for fasting glucose is defined as the mean of the last two non-missing fasting values measured on or prior to Day 1. If only one value is available, then that single value will be used as baseline. Baseline HbA_{1C} is defined as the last non-missing value on or prior to Day 1.

Baseline for lipids parameters (LDL-C, non-HDL-C, TC, HDL-C, TG) is defined as the mean of the last two non-missing fasting values measured on or prior to the *date of randomization*. If only one value is available, then that single value will be used as baseline. If the patient had no fasting values available at baseline, non-fasting values will be used.

Baseline for hs-CRP is defined as the last non-missing value on or prior to the date of randomization.

7.2.4. Analysis Visit Windows

For data analysis purpose, unless otherwise specified, study assessments will be assigned to analysis visits based on the Study Day (Section 7.2.2), and analysis visit windows specified in Appendix 3.

For lipids parameters (LDL-C, non-HDL-C, TC, HDL-C, TG) and hs-CRP, the *date of randomization* will be used as the start date to determine the analysis visit windows. For hs-CRP only, the end-of-study (EOS) measurement is defined as the last measurement taken for the patient.

In cases where multiple assessments fall into the same analysis visit, and only one is used for analysis, it is selected based on the following rules.

- The assessment closest to the target (nominal visit) date will be used.
- If there are ties, the assessment after the target date will be used.
- If multiple values are available with the same date and time, the assessment with larger laboratory accession number (LBREFID) will be used.

Note that unscheduled visits are treated the same way as scheduled visits.

Nominal visits (e.g., S1, S2, T1, etc, see Appendix 1) may be used in listings as appropriate.

7.2.5. Time to Event and Date of Censoring

For time-to-event analysis of clinical endpoint events (including new-onset type 2 diabetes), the start date is the date of randomization when the FAS is used, based on the ITT principle. When the PPS is used, the start date is set to be the date of first dose. For composite endpoints, the event date is the date of the first component event.

Patients who did not have any event in question will be considered as censored for the analysis. The date of censoring is determined as the following:

- Fatal events (CV death, fatal MI, fatal stroke, all-cause mortality): censored at Date of Last Survival Follow-Up.
- Non-fatal events and composite endpoints that include both fatal and non-fatal events: censored at the Date of Last Assessment.

Please see Section 18.3 for special censoring rule as applicable to patients from Ukraine as a result of the ongoing conflict.

7.3. Prior and Concomitant Medications

Prior medications are medications which started and ended prior to Day 1.

Concomitant medications are medications that started after Day 1, or that started before Day 1 and continued through Day 1, or if the status is “ongoing” at Day 1.

7.4. Diabetes Related Definitions

7.4.1. Baseline Glycemic Status

Analyses of diabetes and related biomarkers are conducted with specific subsets of study population based on the baseline glycemic status defined in Table 1.

- For efficacy analyses of new-onset type 2 diabetes (conducted in the study population with No Diabetes at baseline), and related biomarkers HbA1c and fasting glucose, the FAS (or PPS for sensitivity analyses) is used with subpopulations defined according to the baseline glycemic status.
- For safety analyses of AESIs of *new-onset diabetes* (conducted in the study population with No Diabetes at baseline), and *worsening hyperglycemia* (Diabetes at baseline), and related safety laboratory measures including HbA1c and fasting glucose, the SAS is used with subpopulations defined according to the baseline glycemic status.

Table 1: Baseline Glycemic Status

Status	Definition
Diabetes	Meeting 1 or more of the following criteria at baseline captured by information recorded prior to Day 1: 
 • Medical history or adverse events indicating diabetes as defined in the Diabetes Committee Charter (attached as Appendix 8) • Prior glucose-lowering medication as defined by the Diabetes Committee Charter (attached as Appendix 8) • HbA_{1C} measurement $\geq 6.5\%$ • Two or more measurements of fasting glucose ≥ 126 mg/dL (7.0 mmol/L)
Inadequately Controlled (IC) Diabetes	With Diabetes and a HbA _{1C} of 7% or greater at baseline.
No Diabetes	Not meeting any of the criteria for Diabetes at baseline.
Prediabetes	No Diabetes at baseline, and with: 
 • HbA_{1C} measurement of $\geq 5.7\%$ and $< 6.5\%$, OR • 1 or more measurements of fasting glucose ≥ 100 mg/dL (5.6 mmol/L), but not more than 1 value of fasting glucose ≥ 126 mg/dL (7.0 mmol/L).
Normoglycemia	No Diabetes, and not meeting the criteria for Prediabetes at baseline.

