10.6.3. Treatment Week 0 (Visit T1; Day 1)

Prior to scheduling Visit T1, screening clinical results will be reviewed to determine whether the patient continues to meet lab eligibility criteria. At Visit T1, adherence to and tolerability with placebo IMP during the Run-in Period ($\geq 80\%$ adherence required) will be assessed. Patients with intolerable side effects, including but not limited to muscular skeletal pain, will be run-in failures.

If the patient has met all inclusion criteria and none of the exclusion criteria, the patient may be randomized into the double-blind Treatment Period. Patients who fail to meet all entry criteria after initiation of single-blind run-in IMP are considered to be run-in failures and will not be randomized.

Patients are considered randomized once all eligibility criteria are confirmed and a randomization number is obtained by the IWRS on the day of first dose.

The patient will undergo the following assessments and procedures at Day 1 (Visit T1):

- Concomitant medication review (ongoing)
- Assess AEs, SAEs, and potential clinical endpoints
- Return of unused single-blind IMP and assessment of IMP dosing adherence
- Assessment of tolerability of IMP and continued interest in study participation
- Review inclusion/exclusion criteria to establish patient eligibility
- Weight
- Vital signs

- Central clinical laboratory evaluations:
 - Hematology, blood chemistry, and urinalysis
 - Basic fasting lipids (TC, calculated LDL-C, HDL-C, non-HDL-C, and TG) and hs-CRP
- Urine pregnancy test (in female patients of childbearing potential)
- IWRS contact to obtain the patient randomization number and MED ID number for double-blind IMP
- Dispense double-blind IMP and provide dosing and storage instructions
- Diet and exercise counselling
- Schedule next visit

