15.3.2. Secondary Efficacy Endpoint Time to NODM

All potential events of NODM are reviewed and verified by the Diabetes Committee in a blinded fashion according to the Diabetes Committee Charter. All events that were reviewed will be presented in a listing. Only verified NODMs are analyzed as efficacy endpoints.

The time to first occurrence of new onset type 2 diabetes mellitus during study will be analyzed by a Cox PH model for the patients with baseline glycemic status (Section 7.4) of no diabetes in the FAS and its subcategories of prediabetes and normoglycemia. The prediabetes subgroup is considered as the primary analysis for this endpoint. The onset date of NODM will be the earliest date of the event as verified by the Diabetes Committee.

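### SAP Table 1's Diabetes row is worded to leave out the Visit T1 fasting glucose, so its two-value glucose criterion cannot be met from scheduled visits and conflicts with the SAP's own baseline definition

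*SAP*

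**What the plan says.** SAP 7.4.1, Table 1, defines Diabetes as "Meeting 1 or more of the following criteria at baseline captured by information recorded prior to Day 1". There are four alternative criteria: history or adverse events indicating diabetes, glucose-lowering medication, HbA1c of at least 6.5%, and "Two or more measurements of fasting glucose" at or above 126 mg/dL. No Diabetes is the complement of Diabetes. Prediabetes and Normoglycemia are subdivisions of No Diabetes, and neither row repeats the before-Day-1 limit.

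SAP 7.2.2 fixes the reference date: "Day 1 (Reference Start Date) is defined as the Date of First Dose of IMP". Protocol 10.6.3 places it at Visit T1, because "a randomization number is obtained by the IWRS on the day of first dose".

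Two other parts of the SAP treat T1 as baseline. Section 7.2.3 says: "Baseline for fasting glucose is defined as the mean of the last two non-missing fasting values measured on or prior to Day 1". Appendix 3 gives T1, on Day 1 before the first dose, as the baseline visit for glucose. Protocol 15.4 applies the same two-value criterion at baseline, with no before-Day-1 limit.

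For the NODM endpoint, SAP 15.3.2 states: "The prediabetes subgroup is considered as the primary analysis for this endpoint".

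**The concern.** A criterion that needs two fasting glucose values is tied to a window that holds only one scheduled value. A patient with two qualifying values before any study drug can then be placed in No Diabetes and counted as at risk of new-onset diabetes. Full chemistry is next drawn at Month 3, so such a patient could appear as an early event that reflects baseline status rather than treatment. In both arms this would tend to pull the NODM ratio toward 1.

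The same classification sets the population for the NODM adverse event of special interest (AESI) in SAP 16.1.2, where dilution toward 1 is not reassuring. It also defines the HbA1c and fasting glucose strata and one MACE subgroup factor.

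**Working it through.** The plan gives no figure to reproduce here. The check is a count of scheduled draws, then a worked patient, then an illustration of size.

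**1. Scheduled pre-dose fasting glucose.** Glucose belongs to the fasting chemistry panel (Protocol Table 4). Visit contents are from Protocol 10.6.1 to 10.6.3 and Appendix 1. At T1 the central laboratory list includes "Hematology, blood chemistry, and urinalysis".

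| Visit | Timing | Glucose scheduled | Counts under Table 1, Diabetes row | Counts under SAP 7.2.3 |
|---|---|---|---|---|
| S1 | Week -5 | yes | yes | yes |
| S2 | Week -4 | no (lipids and serology) | – | – |
| T1 | Day 1, pre-dose | yes | no | yes |
| Total | | 2 | 1 | 2 |

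With one scheduled value, two or more cannot be reached on the schedule.

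**2. Unscheduled routes to a second value.** Protocol 10.6.1 allows optional repeats between S1 and T1 for blood pressure, TSH, eGFR, ALT, AST and CK; glucose is not named. Protocol 10.5 requires screening procedures to be repeated on rescreening. Either could supply a second value before Day 1, but only for some patients.

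**3. Worked patient.** S1 132 mg/dL, T1 138 mg/dL, HbA1c 6.3%, no history, no medication.

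- SAP 7.2.3: baseline glucose = (132 + 138)/2 = 135 mg/dL.
- Table 1 as worded: one value of at least 126, so not Diabetes; HbA1c lies between 5.7% and 6.5%, so Prediabetes.
- Table 1 with T1 counted: two values of at least 126, so Diabetes.
- With HbA1c 6.6% instead, both readings give Diabetes, because HbA1c is drawn at S1.

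If HbA1c were 5.5%, the label would depend on which window the Prediabetes row uses. Counting S1 alone gives Prediabetes. Counting both values breaches that row's limit of one value of at least 126 and leaves Normoglycemia by default. Either way the patient sits in No Diabetes.

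**4. Size, under assumptions.** The documents give no rates. Let f be the share of the Prediabetes group with both pre-dose values at least 126 and HbA1c below 6.5%, assumed 1% to 3%. Let r be the true placebo NODM incidence, assumed 8% to 12%. Suppose every such patient becomes a counted event in both arms.

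- Share of placebo events = f/(f + r): lowest 0.01/0.13 = 8%, highest 0.03/0.11 = 27%.
- Observed ratio = (HR × r + f)/(r + f).
  - True 0.80: (0.096 + 0.01)/0.13 = 0.815 to (0.064 + 0.03)/0.11 = 0.855.
  - True 0.85: (0.102 + 0.01)/0.13 = 0.86 to (0.068 + 0.03)/0.11 = 0.89.

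A second form needs no incidence. If a share x of placebo events comes from misclassified patients with ratio 1, a true 0.85 reads 0.85(1 − x) + x. For x = 1%, 5%, 10% and 20% this is about 0.852, 0.858, 0.865 and 0.880.

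**The case against.** The strongest reply is that the SAP does not consistently exclude T1. The Table 1 sentence itself refers to baseline, SAP 7.2.3 and Appendix 3 include Day 1 pre-dose values, and a two-value criterion makes little sense unless S1 and T1 both count. A programmer would have good grounds to include T1. This stands as a reason to treat the matter as an internal contradiction rather than a settled exclusion. It does not remove the problem: Table 1 is the specific rule for glycemic status, and Protocol 15.1 lets the SAP override the protocol's unrestricted wording.

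A reader might infer that prevalent diabetes in general enters the NODM population. The documents do not support that. History, medication and HbA1c still operate, so only patients whose sole evidence is two glucose values of at least 126 are at issue.

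A reader might also infer that the Normoglycemia–Prediabetes boundary shifts, or that the Prediabetes limit of one value of at least 126 can never bind. Neither is established, because the before-Day-1 phrase appears only in the Diabetes row.

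Finally, the Diabetes Committee's review starts at consent and uses the laboratory database (Protocol 11.3), and only verified events count for efficacy (SAP 15.3.2). It may decline to call such a case new-onset. That limits the effect on events, but nothing in the documents says that verification changes the at-risk population.

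**Conclusion.** The contradiction is real and should be corrected. Followed as worded, the Diabetes row misclassifies a specific group: two pre-dose fasting glucose values of at least 126 mg/dL, HbA1c below 6.5%, no history, no medication, and no second glucose value before Day 1.

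The number of such patients cannot be derived from the documents. The illustrated shifts are an upper bound within the assumed inputs, because they require every misclassified patient to become a counted event that treatment does not influence. They should not be read as a predicted bias.

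Status rests on pre-randomization data, so imbalance between arms is not expected. The risk is dilution rather than a raised type I error. NODM lies outside the testing hierarchy (SAP 8.3) with nominal p-values, and the primary and key secondary tests are untouched. The NODM AESI uses a broader event definition, but its population comes from the same table.

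**What to change.** In the Diabetes row of SAP Table 1, replace the restriction to records before Day 1 with: *recorded on or before Day 1 and before the first dose of double-blind IMP*. Add one sentence stating that the same pre-dose window defines the glucose values used in the Prediabetes and Normoglycemia rows, consistent with SAP 7.2.3 and Appendix 3. Make the change before unblinding, since SAP section 6 requires analysis-set membership to be final by then.

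The cost is one phrase, one sentence and a programming condition; the T1 glucose is already collected. The downside is a slightly smaller No Diabetes group and possibly fewer NODM events. If the programs already count T1, the edit only brings the text into line.
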